### 11.5.3 Adverse Events

All reported treatment-emergent AEs will be summarized by treatment group, the number of subjects reporting events, system organ class, preferred term, severity, relationship to study product, and seriousness. When summarizing AEs by causality and severity, each subject will be counted only once within a system organ class or a preferred term by using the event with the greatest relationship and highest severity within each classification.

Serious adverse events (SAEs) will be summarized by severity and relationship to study product, and SAEs will be listed by subject. In addition, a list of subjects who prematurely discontinued from the study due to an AE will be provided.

All information pertaining to AEs noted during the study will be listed by subject, detailing verbatim term given by the Investigator, preferred term, system organ class, onset date, resolution date, maximum severity, seriousness, action taken regarding study product, corrective treatment, outcome, and drug relatedness. The event onset will also be shown relative (in number of days) to date of first administration.

AEs related to study procedures done before study product administration will be provided in a data listing.

### 11.5.4 Vital Signs

Changes from Baseline in vital signs (blood pressure, pulse rate) will be summarized at each evaluation.

### 11.5.5 Physical Examination and EKG

Physical examinations (HEENT, lungs, heart, abdomen, skin, and neurologic) will be performed for all subjects at Baseline (Visit 2) and Week 12 (Visit 5). EKGs will be performed for all subjects at Baseline (Visit 2), Week 4 (Visit 3), and Week 12 (Visit 5). Results will be presented in subject data listings.

---

### 11.5.6 Safety Laboratory Values

Hematology/chemistry/urinalysis safety labs will be performed for all subjects at Baseline (Visit 2), Week 4 (Visit 3), and Week 12 (Visit 5). Urine pregnancy tests will be performed at all visits for female subjects of child bearing potential, and will be presented in subject data listings.

#### Subset Analyses

Subgroup analyses will be done based on age (above 65 years vs below 65 years), median age, gender, race, ethnicity, location of treated lesion(s) on the face and/or scalp and previous treatment of AK (naïve vs experienced).

### 11.6 Analysis of Drug Concentrations

Analysis of drug concentration will not be done in this study.

### 11.7 Statistical Analysis Plan

A Statistical Analysis Plan, describing all statistical analyses, will be provided as a separate document prior to database lock.

## APPENDIX 1 - Declaration of Helsinki (2013)

*Adopted by the 18th WMA General Assembly, Helsinki, Finland, June 1964, and amended by the:  
29th WMA General Assembly, Tokyo, Japan, October 1975  
35th WMA General Assembly, Venice, Italy, October 1983  
41st WMA General Assembly, Hong Kong, September 1989  
48th WMA General Assembly, Somerset West, Republic of South Africa, October 1996  
52nd WMA General Assembly, Edinburgh, Scotland, October 2000  
53rd WMA General Assembly, Washington 2002 (Note of Clarification on paragraph 29 added)  
55th WMA General Assembly, Tokyo 2004 (Note of Clarification on Paragraph 30 added)  
59th WMA General Assembly, Seoul, October 2008  
64th WMA General Assembly, Fortaleza, Brazil, October 2013*

### A. PREAMBLE

1. The World Medical Association (WMA) has developed the Declaration of Helsinki as a statement of ethical principles for medical research involving human patients, including research on identifiable human material and data.  
The Declaration is intended to be read as a whole and each of its constituent paragraphs should be applied with consideration of all other relevant paragraphs.
2. Consistent with the mandate of the WMA, the Declaration is addressed primarily to physicians. The WMA encourages others who are involved in medical research involving human patients to adopt these principles.

### B. GENERAL PRINCIPLES

3. The Declaration of Geneva of the WMA binds the physician with the words, "The health of my patient will be my first consideration," and the international Code of Medical Ethics declares that, "A physician shall act in the patient's best interest when providing medical care."
4. It is the duty of the physician to promote and safeguard the health, well-being and rights of patients, including those who are involved in medical research. The physician's knowledge and conscience are dedicated to the fulfillment of this duty.
5. Medical progress is based on research that ultimately must include studies involving human patients.
6. The primary purpose of medical research involving human patients is to understand the causes, development and effects of diseases and improve preventive, diagnostic and therapeutic interventions (methods, procedures and treatments). Even the best current interventions must be evaluated continually through research for their safety, effectiveness, efficiency, accessibility and quality.
7. Medical research is patient to ethical standards that promote and ensure respect for all human patients and protect their health and rights.
8. While the primary purpose of medical research is to generate new knowledge, this goal can never take precedence over the rights and interests of individual research patients.
9. It is the duty of physicians who are involved in medical research to protect the life, health, dignity, integrity, right to self-determination, privacy, and confidentiality of personal information of research patients. The responsibility for the protection of research patients must always rest with the physician or other health care professionals and never with the research patients, even though they have given consent.
10. Physicians must consider the ethical, legal and regulatory norms and standards for research involving human patients in their own countries as well as applicable international norms and standards. No national or international ethical, legal or regulatory requirement should reduce or eliminate any of the protections for research patients set forth in this Declaration.
11. Medical research should be conducted in a manner that minimizes possible harm to the environment.

12. Medical research involving human patients must be conducted only by individuals with the appropriate ethics and scientific education, training and qualifications. Research on patients or healthy volunteers requires the supervision of a competent and appropriately qualified physician or other health care professional.
13. Groups that are underrepresented in medical research should be provided appropriate access to participation in research.
14. Physicians who combine medical research with medical care should involve their patients in research only to the extent that this is justified by its potential preventive, diagnostic or therapeutic value and if the physician has good reason to believe that participation in the research study will not adversely affect the health of the patients who serve as research patients.
15. Appropriate compensation and treatment for patients who are harmed as a result of participating in research must be ensured.

**C. RISK, BURDENS AND BENEFITS**

16. In medical practice and in medical research, most interventions involve risks and burdens. Medical research involving human patients may only be conducted if the importance of the objective outweighs the risks and burdens to the research patients.
17. All medical research involving human patients must be preceded by careful assessment of predictable risks and burdens to the individuals and groups involved in the research in comparison with foreseeable benefits to them and to other individuals or groups affected by the condition under investigation. Measures to minimize the risks must be implemented. The risks must be continuously monitored, assessed and documented by the researcher.

18. Physicians may not be involved in a research study involving human patients unless they are confident that the risks have been adequately assessed and can be satisfactorily managed.

When the risks are found to outweigh the potential benefits or when there is conclusive proof of definitive outcomes, physicians must assess whether to continue, modify or immediately stop the study.

**D. VULNERABLE GROUPS AND INDIVIDUALS**

19. Some groups and individuals are particularly vulnerable and may have an increased likelihood of being wronged or of incurring additional harm.

All vulnerable groups and individuals should receive specifically considered protection.

20. Medical Research with a vulnerable group is only justified if the research is responsive to the health needs or priorities of this group and the research cannot be carried out in a non-vulnerable group. In addition, this group should stand to benefit from the knowledge, practices or interventions that result from the research.

**E. SCIENTIFIC REQUIREMENTS AND RESEARCH PROTOCOLS**

21. Medical research involving human patients must conform to generally accepted scientific principles, be based on a thorough knowledge of the scientific literature, other relevant sources of information, and adequate laboratory and, as appropriate, animal experimentation. The welfare of animals used for research must be respected.
22. The design and performance of each research study involving human patients must be clearly described and justified in a research protocol. The protocol should contain a statement of the ethical considerations involved and should indicate how the principles in this Declaration have been addressed. The protocol should include information regarding funding, sponsors, institutional

---

affiliations, potential conflicts of interest, incentives for patients and information regarding provisions for treating and/or compensating patients who are harmed as a consequence of participation in the research study. In clinical trials, the protocol must also describe appropriate arrangements for post-trial provisions.

#### F. RESEARCH ETHICS COMMITTEES

23. The research protocol must be submitted for consideration, comment, guidance and approval to the concerned research ethics committee before the study begins. This committee must be transparent in its functioning, must be independent of the researcher, the sponsor and any other undue influence and must be duly qualified. It must take into consideration the laws and regulations of the country or countries in which the research is to be performed as well as applicable international norms and standards but these must not be allowed to reduce or eliminate any of the protections for research patients set forth in this Declaration. The committee must have the right to monitor ongoing studies. The researcher must provide monitoring information to the committee, especially information about any serious adverse events. No amendment to the protocol may be made without consideration and approval by the committee. After the end of the study, the researchers must submit a final report to the committee containing a summary of the study's findings and conclusions.

#### G. PRIVACY AND CONFIDENTIALITY

24. Every precaution must be taken to protect the privacy of research patients and the confidentiality of their personal information.

#### H. INFORMED CONSENT

25. Participation by individuals capable of giving informed consent as patients in medical research must be voluntary. Although it may be appropriate to consult family members or community leaders, no individual capable of giving informed consent may be enrolled in a research study unless he or she freely agrees.
26. In medical research involving human patients capable of giving informed consent, each potential patient must be adequately informed of the aims, methods, sources of funding, any possible conflicts of interest, institutional affiliations of the researcher, the anticipated benefits and potential risks of the study and the discomfort it may entail, post-study provisions and any other relevant aspects of the study. The potential patient must be informed of the right to refuse to participate in the study or to withdraw consent to participate at any time without reprisal. Special attention should be given to the specific information needs of individual potential patients as well as to the methods used to deliver the information. After ensuring that the potential patient has understood the information, the physician or another appropriately qualified individual must then seek the potential patient's freely-given informed consent, preferably in writing. If the consent cannot be expressed in writing, the non-written consent must be formally documented and witnessed. All medical research patients should be given the option of being informed about the general outcome and results of the study.
27. When seeking informed consent for participation in a research study the physician should be particularly cautious if the potential patient is in a dependent relationship with the physician or may consent under duress. In such situations the informed consent should be sought by an appropriately qualified individual who is completely independent of this relationship.
28. For a potential research patient who is incapable of giving informed consent, the physician must seek informed consent from the legally authorized representative. These individuals must not be included in a research study that has no likelihood of benefit for them unless it is intended to promote the health of the group represented by the potential patient, the research cannot instead be performed with persons capable of providing informed consent, and the research entails only minimal risk and minimal burden.

29. When a potential research patient who is deemed incapable of giving informed consent is able to give assent to decisions about participation in research, the physician must seek that assent in addition to the consent of the legally authorized representative. The potential patient's dissent should be respected.
30. Research involving patients who are physically or mentally incapable of giving consent, for example, unconscious patients, may be done only if the physical or mental condition that prevents giving informed consent is a necessary characteristic of the research group. In such circumstances the physician must seek informed consent from the legally authorized representative. If no such representative is available and if the research cannot be delayed, the study may proceed without informed consent provided that the specific reasons for involving patients with a condition that renders them unable to give informed consent have been stated in the research protocol and the study has been approved by a research ethics committee. Consent to remain in the research should be obtained as soon as possible from the patient or a legally authorized representative.
31. The physician must fully inform the patient which aspects of their care are related to the research. The refusal of a patient to participate in a study or the patient's decision to withdraw from the study must never adversely affect the patient-physician relationship.
32. For medical research using identifiable human material or data, such as research on material or data contained in biobanks or similar repositories, physicians must seek informed consent for its collection, storage and/or reuse. There may be exceptional situations where consent would be impossible or impracticable to obtain for such research. In such situations the research may be done only after consideration and approval of a research ethics committee.

#### I. USE OF PLACEBO

33. The benefits, risks, burdens and effectiveness of a new intervention must be tested against those of the best proven intervention(s), except in the following circumstances:
  - a. Where no proven intervention exists, the use of placebo, or no intervention, is acceptable; or
  - b. Where for compelling and scientifically sound methodological reasons the use of any intervention less effective than the best proven one, the use of placebo, or no intervention is necessary to determine the efficacy or safety of an intervention and the patients who receive any intervention less effective than the best proven one, placebo, or no intervention will not be patient to additional risks of serious or irreversible harm as a result of not receiving the best proven intervention. Extreme care must be taken to avoid abuse of this option.

#### J. POST-TRIAL PROVISIONS

34. In advance of a clinical trial, sponsors, researchers and host country governments should make provisions for post-trial access for all participants who still need an intervention identified as beneficial in the trial. This information must also be disclosed to participants during the informed consent process.

#### K. RESEARCH REGISTRATION AND PUBLICATION AND DISSEMINATION OF RESULTS

35. Every research study involving human patients must be registered in a publicly accessible database before recruitment of the first patient.
36. Researchers, authors, sponsors, editors and publishers all have ethical obligations with regard to the publication and dissemination of the results of research. Researchers have a duty to make publicly available the results of their research on human patients and are accountable for the completeness and accuracy of their reports. All parties should adhere to accepted guidelines for ethical reporting. Negative and inconclusive as well as positive results must be published or otherwise made publicly available. Sources of funding, institutional affiliations and conflicts of interest should be declared in the publication. Reports of research not in accordance with the principles of this Declaration should not be accepted for publication.
37. In the treatment of an individual patient, where proven interventions do not exist or other known interventions have been ineffective, the physician, after seeking expert advice, with informed consent

from the patient or a legally authorized representative, may use an unproven intervention if in the physician's judgment it offers hope of saving life, re-establishing health or alleviating suffering. This intervention should subsequently be made the object of research, designed to evaluate its safety and efficacy. In all cases, new information must be recorded and, where appropriate, made publicly available.

October 2013

**APPENDIX 2 – Hematology, Chemistry, and Urinalysis List of Laboratory Tests**

Hematology	Hemoglobin, Hematocrit, RBC, WBC (total count and differential count), Platelets Count, Mean Platelet Volume (MPV), MCV, MCH, MCHC, RDW, Neutrophils (absolute value and %), Bands (ABS CNT), Bands, Lymphocytes (absolute value and %), Monocytes (absolute value and %), Eosinophils (absolute value and %), Basophils (absolute value and %), RBC Morphology
Comprehensive Metabolic Panel	Sodium, Potassium, Glucose, BUN, Creatinine, BUN/Creatinine, Chloride, Calcium, Protein, Albumin, Globulin (total), A/G Ratio, SGOT (AST), SGPT (ALT), Bilirubin (total), Alkaline Phosphatase, Basic Metabolic Panel
Urinalysis	Color, Character, Specific Gravity, pH, Protein, Glucose, Ketone, Urobilinogen, Bilirubin, Blood, Mucous Threads, Leukocyte Esterase, Amorphous Sediment, Nitrite, Urine Comment, RBC, WBC, Epithelial Cells, Crystals, Casts, Bacteria

1.1. Scope

This document contains detailed information on the statistical analyses proposed to be performed on the data collected in the trial DFD-07-CD-002, to aid the production of the Clinical Trial Report (CTR) including summary tables and listings. The contents of this document were reviewed by the sponsor, [name], Ltd., and the trial biostatistician at Integrium.

1.2. Study Background/Plan

This is a multi-center, randomized, double-blind, parallel group, Vehicle-controlled study. The study products will be applied to a single continuous 5 cm x 5 cm (25cm²) treatment area containing the target AK lesions once or twice daily for a duration of 12 weeks of treatment, followed by a 4-week treatment-free follow-up. Subjects, who are at least 18 years old, diagnosed with AK of the face and/or scalp will be randomized to treatment in one of the four arms (60 subjects in each group).

Subjects will receive either 1.25% concentration once daily (with Vehicle once daily), 2.5% concentration once daily (with Vehicle once daily), 2.5% concentration twice daily or Vehicle twice daily.

The study consists of three phases: Screening (up to 60 days), Treatment (12 weeks) and Follow-Up (4 weeks).

1.3. Trial Objectives and Purpose

The objective of this study is to evaluate the dose response relationship of the efficacy and safety of two strengths of topical DFD-07 (celecoxib) Cream, 1.25% and 2.5% when used once or twice daily compared to Vehicle in the treatment of AK of the face and/or scalp over a 12-week period with a 4-week follow up.

1.3.1. Primary Efficacy Endpoint

The proportion of subjects with complete clearance of AK lesions at the End of Study Visit, at 16 weeks (absence of clinically visible or palpable AK lesions in the treatment area) for DFD-07 (celecoxib) Cream, 2.5% BID compared to Vehicle Cream.

1.3.2. Secondary Efficacy Endpoints

The secondary efficacy endpoints for the study are:

1. Proportion of subjects with complete clearance of AK lesions at the End of Study Visit, for DFD-07 (celecoxib) Cream, 2.5% QD compared to Vehicle Cream.
2. Proportion of subjects with complete clearance of AK lesions at the End of Study Visit, for DFD-07 (celecoxib) Cream, 1.25% QD compared to Vehicle Cream.
3. Proportion of subjects with complete clearance of AK lesions at Week 12 in the different treatment groups.
4. Proportion of subjects with complete clearance of AK lesions at Week 8 in the different treatment groups.

5. Proportion of subjects with partial clearance of AK lesions at Week 4, 8, 12, and 16 in the different treatment groups (partial clearance defined as at least a 75% reduction in the number of AK lesions in the treatment area compared to Baseline).
6. Percent change from baseline in AK lesion count at Week 4, 8, 12 and 16 in the different treatment groups.
7. Number and proportion of subjects with local skin reactions in the different treatment groups.

2. Detailed Statistical Methods

2.1. General Statistical Methods

Efficacy summaries will be provided for the Intention to Treat and Per Protocol Populations. Safety summaries will be provided for the Safety Population.

Descriptive statistics (N, arithmetic means, SD, minimum, median, maximum) for all continuous values and frequency tables for categorical variables will be created. With regard to primary and secondary objectives as descriptive statistical evaluation, absolute and relative frequencies of number of observations will be presented together with 95% confidence intervals on the proportion of success and the difference compared to Vehicle Cream.

If the method to handle missing observations is not explicitly defined (i.e. Percent Change from Baseline in Actinic Keratosis Lesion Count), two principles will be applied to adjust for missing observations: last observation carried forward (LOCF) and multiple imputations (MI). Last observation carried forward will be derived in the analysis datasets while the multiple imputations method will be performed using SAS procedures PROC MI and PROC MIANALYZE.

If there are at least 5 observations in each cell in the 2 x 2 table (when comparing treatment groups to Vehicle), the Pearson's Chi Square test will be used. If there are not at least 5 observations in each cell in the 2 x 2 table (when comparing treatment groups to Vehicle), the Fisher's exact test will be used.

A Documentation of Statistical Decisions will be created, reviewed and signed (with appropriate signatures) prior to database lock. This document will document:

- On a subject level, which populations the subject is included in and reason for exclusion if a subject is excluded from a population.
- The details of any decision made (i.e. how data is handled in the analysis or the addition of any outputs) based on the actual data collected.
- Any known issues with the data quality and how that data is handled in the analysis, and
- Any other unexpected findings that require documentation prior to database lock.

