### 5.2 Inclusion Criteria

1. Subject understands the study procedures, is willing to comply with the study procedures and required visits, and agrees to participate by giving written informed consent. Subjects with a legal guardian, must have the written informed consent of the legal guardian.
2. Subject (or legal guardian) must be willing to authorize use and disclosure of protected health information collected for the study.
3. Subjects must have 5 or more AK lesions that are non-hypertrophic and non-hyperkeratotic, contained within a single contiguous approximately 5 cm x 5 cm (25 cm^2) region of face and/or scalp.
4. Subjects must be 18 years of age or older. Male and female subjects can be enrolled.
5. Female subjects of childbearing potential must agree to use contraception during the study which can include abstinence with an adequate secondary option should the subject become sexually active. All women of childbearing potential must complete a urine pregnancy test (test must have a sensitivity of at least 25mIU/ml for human chorionic gonadotropin) at the Baseline Visit (Visit 2) and the test result must be negative to be eligible for enrollment.

A female is considered of childbearing potential unless she is:

- postmenopausal for at least 12 months prior to study product administration;
- without a uterus and/or both ovaries; or has been surgically sterile (i.e., tubal ligation) for at least 6 months prior to study product administration.

Reliable methods of contraception are:

- hormonal methods or intrauterine device in use  $\geq$  90 days prior to study product administration; or
- barrier methods plus spermicide in use at least 14 days prior to study product administration.
- partner has had a vasectomy at least 3 months previous to study product administration.
- Essure®

**Exception:** Sexually inactive female subjects of childbearing potential are not required to practice a reliable method of contraception and may be enrolled at the investigator's discretion provided that they are counseled to remain sexually inactive for the duration of the study and understand the possible risks involved in getting pregnant during the

study. An abstinent female must agree that if she becomes sexually active during the study she will use an acceptable form of contraception.

6. Subjects must be able to have  $\geq 60$  days washout from prohibited medications:

- Masoprolol
- 5-Fluorouracil
- Cyclosporin

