2.4. Study Conduct and Baseline Characteristics

2.4.1. Demographics and Subject Baseline Characteristics

Subject demographics and baseline data characteristics will be reported in descriptive summaries by treatment group for the Intention-to-Treat, Per Protocol and Safety populations. Data will also be shown in data listings by treatment group and subject.

Evaluation for significance of the comparisons of the individual baseline characteristics between treatment groups will be performed using an analysis of variance model (for continuous data) or Fisher's exact test (for categorical data).

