2.6. Efficacy

Primary endpoint

For statistical assessment of the primary endpoint with a significance level of 0.05 the following underlying hypotheses are used:

$H_0: p_1 \leq p_2$ vs. $H_a: p_1 > p_2$

Where p_1 is the treatment effect of 2.5% DFD-07 (celecoxib) Cream twice daily and p_2 is the treatment effect of the Vehicle Cream preparation.

Secondary endpoints

For statistical assessment of all product comparisons after certain period of treatment (i.e. at Visits 3, 4, 5 and 6) with a significance level of 0.05, the following underlying hypotheses are used:

$H_0: p_1 \leq p_2$ vs. $H_a: p_1 > p_2$

Where p_1 is the treatment effect of 1.25% or 2.5% DFD-07 (celecoxib) Cream once daily and p_2 is the treatment effect of the Vehicle Cream preparation.

For the percent change from baseline in AK lesion counts, the Mann-Whitney U-test (Wilcoxon rank sum test) will be used to test for treatment differences compared to the Vehicle Cream preparation at a significance level of 0.05.

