2.8. Sample Size and Power Considerations

The sample size estimation of this trial is based on the assumption that the Active product exhibits a complete clearance of the AK lesions in 45% of the subjects, while the Vehicle does so in 20% of the subjects (a difference of 25% between active and Vehicle treatment groups). Assuming a power of 80% and α of 0.05, in order to demonstrate the statistical significance of such an effect difference, 54 patients per treatment group would be needed.

Considering the exploratory dose-response character of the trial, and assuming a drop-out rate of 10%, 60 subjects need to be recruited in each treatment group. With 4 treatment groups in the study, it is planned to recruit approximately 240 subjects in the study.

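### The primary clearance test is valid but leaves out baseline lesion count; pre-specifying adjustment for it is a cheap improvement of uncertain, probably small, size

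*SAP*

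**What the plan says.** **Test.** SAP 2.1 uses Pearson's chi-square under the condition "If there are at least 5 observations in each cell in the 2 x 2 table (when comparing treatment groups to Vehicle"; otherwise it uses Fisher's exact test. It also promises 95% confidence intervals for each proportion and for the difference from Vehicle. SAP 2.6 ("For statistical assessment of the primary endpoint with a significance level of 0.05 the following underlying hypotheses are used") names no covariate. Protocol 11.4 likewise names only unadjusted tests.

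**Endpoint and entry.** Success at Week 16 is no visible or palpable lesion in the treatment area (SAP 1.3.1), and new lesions count against it (Protocol 7.3). On entry, Protocol 5.2 says "Subjects must have 5 or more AK lesions that are non-hypertrophic and non-hyperkeratotic" and sets no ceiling.

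**Baseline count.** Protocol 7.10.2 has the investigator count lesions at Visit 2 in the step before randomisation. Randomisation is stratified by site only (Protocol 6.5). Count is not among the subgroup factors in SAP 2.3.

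**Use of baseline data.** SAP 2.4.1 plans descriptive summaries and adds: "Evaluation for significance of the comparisons of the individual baseline characteristics between treatment groups will be performed", by analysis of variance or Fisher's test. No efficacy analysis draws on those p-values.

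**The concern.** A subject who starts with 15 lesions has more to clear than one who starts with 5. If that makes starting count predictive of success, the unadjusted comparison carries avoidable variance. A chance difference in count between the 2.5% BID and Vehicle arms would then also pass into the estimated difference. The SAP would display such an imbalance but has no pre-specified way to deal with it, and an adjustment chosen after seeing it would not be credible.

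**Working it through.** **1. The plan's own figure.** Inputs (SAP 2.8): 45% vs 20%, power 80%, α 0.05. With pooled variance and no continuity correction:

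n = [z₀.₉₇₅·√(2·0.325·0.675) + z₀.₈₀·√(0.45·0.55 + 0.20·0.80)]² / 0.25²
= [1.960·0.6624 + 0.8416·0.6384]² / 0.0625 = 1.8355² / 0.0625 = 53.9, so 54.

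54 / 0.9 = 60, as stated. This uses two-sided 0.05. The hypotheses in SAP 2.6 are written one-sided; one-sided 0.05 would give 43. That is a separate matter, and two-sided 0.05 is used below.

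Power at 60 per arm: Φ[(0.25·√60 − 1.2982) / 0.6384] = Φ(1.000) = 84.1%.

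**2. Why the count may be prognostic.** If lesions cleared independently with probability 0.9 (an illustration only), all-clear would be 0.9⁵ = 59%, 0.9¹⁰ = 35% and 0.9¹⁵ = 21%. Correlation between lesions in one subject weakens this. With a within-subject correlation of 0.6 and a narrow spread of counts, Vehicle clearance is about 22% at 5 lesions and 17% at 10.

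**3. Power, by simulation at 60 per arm, 45% vs 20%.** The count distribution and prognostic strength are assumptions.

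*(a) Counts of 5 plus a negative binomial with mean 3 (SD 2.4).* The adjusted analysis is a standardised risk difference from a logistic model. With 6,000 trials per setting, the Monte Carlo error is √(0.85·0.15/6000) = 0.5 point.

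| Fall in odds of clearance per extra lesion | Unadjusted power | Adjusted power | Relative efficiency |
|---|---|---|---|
| 1.0 (none) | 84–85% | 84.6% | 0.99 |
| 1.2 | 84–85% | 85.7% | 1.03 |
| 1.35 | 84–85% | 87.0% | 1.07 |
| 1.5 | 84–85% | 87.8% | 1.11 |

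Cross-check at 1.35: the effective n is 60·1.07 = 64.2, and Φ[(0.25·√64.2 − 1.2982) / 0.6384] = Φ(1.104) = 86.5%. About 0.5 to 0.8 point of the simulated gain comes from replacing a pooled by an unpooled statistic and owes nothing to the count. Independent lesions at these rates correspond to factors of about 1.20 (45% arm) and 1.31 (20% arm), so 1.35 and 1.5 go beyond independence.

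*(b) Lesion-level clearance with within-subject correlation 0 to 0.6*, counts of 5 plus Poisson (mean 1.5) or 5 plus negative binomial (mean 4), score test. The power change is −0.4 to +2.2 points and relative efficiency 0.99 to 1.06. Only independent lesions with widely spread counts reach 2 points.

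*(c) Very strong prognosis:* an odds ratio of 3.3 per SD of log count gives 91% vs 85%.

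**4. Chance imbalance.** Under (a), the SE of the between-arm difference in mean count is 2.44·√(2/60) = 0.445 lesion. In the 10% of trials most favourable to active, the mean imbalance is about 1.755·0.445 = 0.78 lesion. The first-order slope is ln(factor)·mean(0.2475, 0.16) = ln(factor)·0.204:

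- factor 1.2: 0.182·0.204·0.78 = 2.9 points
- factor 1.35: 0.300·0.204·0.78 = 4.8 points

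Simulated shifts in that tenth of trials are 2 to 5 points under (a) and 0.5 to 4 points under (b). Adjustment leaves less than 1 point.

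**5. Type I error, two-sided 0.05.** For the standardised difference it is 5.4–5.9% under (a), against 4.8–5.5% for chi-square. Under (b) and (c) the figures are 4.8–5.7% and 4.6–5.4%. The adjusted test runs slightly high, so it needs a small-sample correction.

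**The case against.** The strongest reply is that nothing in the plan fails. The chi-square or Fisher test is valid under randomisation. The unadjusted difference is unbiased over randomisation, and its interval already includes variation from chance imbalance. Power at 60 per arm is about 84% against a target of 80%, in a trial the SAP calls exploratory. All of that stands: this is an unused efficiency, not an error.

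Several stronger readings are tempting, and the documents do not support them:

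- **That the endpoint makes the count prognostic and adjustment therefore gains power.** The definition makes a link plausible. No count distribution or clearance-by-count figure is given, and correlated lesions could make the link weak.
- **That adjustment removes chance imbalance.** It does so for this covariate only. Other factors are untouched; whether to reflect site, the sole stratum, is a separate question.
- **That it costs nothing.** A logistic model needs a stated covariate form and a sparse-data rule to stand in for the Fisher provision. Protocol Table 1 cites a Vehicle rate of 2/49 after 30 days of treatment, so sparse cells are realistic at early visits.
- **That baseline data serve only the significance tests in SAP 2.4.1.** Descriptive summaries and subgroup analyses are planned too, and partial clearance and percent change are computed from the baseline count. The rank test ("For the percent change from baseline in AK lesion counts, the Mann-Whitney U-test (Wilcoxon rank sum test) will be used") is therefore not a further instance of the same gap.
- **That the argument carries over to partial clearance.** That endpoint is a 75% reduction relative to baseline, so the every-lesion-must-go reasoning does not apply.

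**Conclusion.** The point holds as a modest, worthwhile improvement to a valid analysis. The power change is about 0 to +3 points, up to roughly +6 if the count is very strongly prognostic, and a loss of up to about half a point if it is not. The clearer benefit is protection in unlucky randomisations: in the tenth most favourable to active, a shift of about 0.5 to 5 points falls to under 1 point. These figures rest on assumed counts, an assumed link to clearance, and the SAP's 45% and 20% with 60 per arm. A reader should not infer that the primary result would be wrong or underpowered without the covariate.

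**What to change.** Before unblinding, amend SAP 2.6 for complete clearance:

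- Fit a logistic model on treatment and baseline lesion count, with the form of the count stated (for example linear or log).
- Standardise it to the marginal difference in proportions against Vehicle, the quantity SAP 2.1 already plans to report. Give a robust 95% interval and test with a small-sample correction.
- Fall back to the existing Pearson/Fisher rule when cells are sparse or the model does not converge, with both triggers defined in advance.
- Keep the unadjusted two-by-two test as a sensitivity analysis.

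The cost is some SAP wording and code, plus a negligible loss of precision if the count proves uninformative. No new data are needed. Extending the model to partial clearance and dropping the baseline p-values in SAP 2.4.1 are optional.
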